**Table 2: Study outcomes and visit timeline**

	Screening	Baseline	Week 2	Month 1	Month 3	Month 6	Month 9	Month 12
Informed consent and eligibility criteria	X	--	--	--	--	--	--	--
Randomization	--	X	--	--	--	--	--	--
Clinical Assessments								
Adherence	--	--	--	X	X	X	X	X
Side Effects (subjective including symptom check list)	--	X	X	X	X	X	X	X
Toxicity labs (BMP)	X	X	X	X	X	X	X	X
Toxicity labs (CBC and hepatic panel)	X	--	--	--	X	X	X	X
HIV RNA level	X	--	--	--	X	X	X	X
Hep Bs Ag & Hep C Ab (results within 1 year acceptable)*	--	X	--	--	--	--	--	--
Lipid panel (results within 1 year acceptable)	--	X	--	--	--	--	--	--
Pregnancy test (during f/u for women of childbearing potential)	X	X	--	--	X	X	X	X
Blood Outcome Measures								
IL-6 levels (plasma)	X	X	--	X	X	X	X	X
CD4+ T-cell count (blood)	X	X	--	X	X	X	X	X
Inflammatory, coagulation and fibrosis plasma biomarkers	--	X	--	--	X	X	--	X
Monocyte and T-cell Immunophenotyping	--	X	--	--	--	X	--	X
Functional Assessment								
Frailty criteria: unintentional weight loss, exhaustion, physical-inactivity, weak-grip and slow-walk	--	X	--	--	--	X	--	X
Tissue Outcome Measures								
LN fibrosis	--	X	--	--	--	--	--	X
LN cellular immune activation	--	X	--	--	--	--	--	X
Stored plasma	X	X	--	X	X	X	X	X
Stored urine	--	X	--	--	--	X	--	X
Stored PBMCs	--	X	--	--	--	X	--	X
*Prior results that do not need repeating include: HCV Ab positive, HBsAg positive, or HBsAb positive along with HBsAg negative								

## 2.7 Sample Size Considerations

### Power for Reduced Inflammation (IL-6 levels)

- The primary analysis will compare baseline-adjusted log IL-6 measurements at 1, 3, 6, 9 and 12 months between treatment groups.
- Standard deviation (SD) data from SMART (n=122; baseline and month 1) and ESPRIT (n=147; baseline and month 12) on participants who were on continuous ART between both time points were used to estimate a log IL-6 SD of 0.74 pg/mL.
- We assumed a 28% reduction in IL-6 with losartan was plausible based on our pilot data and data from HIV negative studies in the general population.

Based on assumptions above, assuming 5% missing data, and considering the potential

clinical risk reduction associated with IL-6 changes of this magnitude (see epidemiologic data, following paragraph), a total sample size of n=110 will be enrolled. With this sample we will have 80% power to detect an absolute reduction of 0.3 log(IL-6), corresponding to a 26% reduction in IL-6, with a two-sided Type I error of 0.05.

Pooled data from 3,766 participants in SMART, ESPRIT and SILCAAT trials who were taking continuous ART with an HIV RNA level <400 copies/mL at entry—a group that resembles our target population—indicate that a 26% lower baseline IL-6 level is associated with a 34% lower risk of serious non-AIDS events or death from any cause.

### **Power for Immune Recovery (CD4+ T-cell count)**

- The primary analysis will consider average changes in log10 blood CD4 levels (total and naïve) over 12 months. Total CD4 count will be measured at 1, 3, 6, 9, and 12 months, and 4 pre-treatment baseline values (2 historical within prior year, 1 screening, 1 baseline) will be averaged to compute baseline CD4+ count for analyses. Averaging multiple baseline measurements will reduce variability and thereby increase statistical power. The log10 naïve CD4+ subset count will be measured at baseline and months 6 and 12.
- Based on participants ≥ age 50 in the SMART and ESPRIT studies (n=510 total), the estimated SD of yearly changes in log10 total CD4+ count is 0.11. Based on preliminary data from [name] lab, the estimated SD of yearly changes in the log10 naïve CD4 subset is 0.24.

With our sample size of n=110, we estimate that we will have 80% power to detect a 9.6% (19.8%) difference in total (naïve) CD4 count. Assuming a baseline total CD4 level of ~300-400 cells/mm^3, a 9.6% increase in CD4 count corresponds to an approximate average annual increase of 30-40 cells per year. From our prior epidemiologic work studying clinical risk based on total CD4+ count in blood after treatment with ART, a difference in this range would correspond to 5-8% difference in risk for a composite of non-AIDS events.

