## **6 ANALYSIS PLAN**

The general goal of this study is to evaluate the potential treatment effects of losartan for reducing systemic inflammation and improving immune recovery. For the effect of losartan on systemic inflammation, the outcome will be the average of log IL-6 levels (plasma) from samples obtained at months, 1, 3, 6, 9, and 12; two pre-treatment log IL-6 measurements will be averaged to estimate baseline log IL-6 level. The primary

analysis will be intention to treat using a linear model for the aforementioned outcomes with treatment group indicator as the main predictor, fitted using the Generalized Estimating Equations approach with an independence working correlation structure. The model will be adjusted for baseline log IL-6 and clinical center. The hypothesis of no treatment effect will be assessed by considering the statistical significance of the treatment group indicator. Additional analyses will consider change in IL-6 at specific visit time points, as well as the percent of participants that achieve an IL-6 level <1.1 pg/mL (i.e., the 25th percentile among HIV+ patients with viral suppression in the SMART/ESPRIT/SILCAAT trials)

Immune recovery will be assessed by modeling log10 CD4+ T-cell counts in blood, using a linear mixed effects model that, in addition to the model components described for the systemic inflammation analysis above, incorporates a main effect for time (in months), a treatment-by-time interaction, and individual-specific intercepts and slopes (for time). The hypothesis of no treatment effect on rate of yearly change in log10 CD4 counts will be evaluated by considering the statistical significance of the treatment-by-time interaction term.

Subgroup analyses will be performed to explore potential for differential treatment effects (e.g., entry CD4 count [including ≥ vs. < 350], CD4:CD8 ratio, use of statins, aspirin, or other drugs with potential anti-inflammatory or anti-fibrotic properties, and co-morbidities or polymorbidities). Trends in treatment effects on the primary outcome (log IL-6) over time will be assessed using linear mixed effects models similar to those described for the modeling of log10 CD4+.

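### The CD4 differences given 80% power in section 2.7 (9.6% total, 19.8% naive) do not follow from the stated SDs, n=110 or the planned slope test, which give about 14–15% and 34% or more

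*Combined protocol and SAP*

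**What the plan says.** Section 2.7, Power for Immune Recovery, takes from earlier trial data on people aged 50 or over that the SD of yearly change in log10 "total CD4+ count is 0.11". It gives 0.24 for the naive subset, from preliminary laboratory data. It then concludes for n=110: "we estimate that we will have 80% power to detect a 9.6% (19.8%) difference in total" (naive) CD4 count. The total CD4 figure is put in absolute terms: "a 9.6% increase in CD4 count corresponds to an approximate average annual increase of 30-40 cells per year", assuming a baseline of about 300–400 cells/mm³. A 5–8% difference in the risk of non-AIDS events is attached to a change of that size.

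On method, the same section says "The primary analysis will consider average changes in log"10 CD4 over 12 months. Total CD4 uses four averaged pre-treatment values and visits at months 1, 3, 6, 9 and 12. Naive CD4 has one baseline value and months 6 and 12. The section adds: "Averaging multiple baseline measurements will reduce variability and thereby increase statistical power". It gives no correlation, variance factor or formula. Alpha appears only under IL-6 ("with a two-sided Type I error of 0.05"), as does the 5% missing-data allowance.

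Section 6 plans a different analysis: a linear mixed model with individual intercepts and slopes, adjusted for baseline. There, "The hypothesis of no treatment effect on rate of yearly change in log"10 "CD4 counts will be evaluated by considering the statistical significance of the treatment-by-time interaction term".

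**The concern.** The detectable differences look too small for the SDs and sample size printed beside them. The analysis that 2.7 describes (average change) is also not the one that section 6 tests (slope), so it is unclear which test the 80% refers to.

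This is the only power statement for the main secondary outcome. If the planned test has roughly even odds of detecting the stated difference, a null CD4 result could be over-read as evidence against a gain of 30–40 cells per year, and the risk statement tied to that gain would be over-read with it.

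**Working it through.** **Inputs.** SDs of yearly change 0.11 and 0.24 log10, 80% power and n=110 (section 2.7, CD4). 1:1 allocation, so 55 per arm (Protocol Summary). Two-sided alpha 0.05 and 5% missing (section 2.7, IL-6), assumed to apply to CD4. Allowing for 5% missing leaves 110 × 0.95 / 2 = 52.25 per arm.

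**1. Trying to reproduce the plan's figures.** For two means, d = (1.960 + 0.842) × SD × √(2/n). At n = 55 the multiplier of SD is 2.802 × 0.1907 = 0.534. The percentage increase is 10^d − 1.

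- Total: d = 0.0588, an increase of 14.5%. With 52.25 per arm, d = 0.0603, or 14.9%.
- Naive: d = 0.1282, an increase of 34.3%. With 52.25 per arm, d = 0.1315, or 35.4%.

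The figure of 120 participants in section 2.1 does not explain the gap: 60 per arm gives 13.8% and 32.7%. The stated 9.6% and 19.8% are not reproduced.

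**2. Power at the stated differences, plain two-sample test.**

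- As increases: log10(1.096) = 0.0398 and log10(1.198) = 0.0785. Power is 47.5% and 40.3% at 55 per arm, and 45.6% and 38.6% at 52.25. Reaching 80% would take about 120 and 147 per arm.
- As decreases: −log10(0.904) = 0.0438 and −log10(0.802) = 0.0958. Power is about 55% for both at 55 per arm, and about 53% at 52.25.

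**3. The section 6 slope test, total CD4.** With visits at months 1, 3, 6, 9 and 12 expressed in years, the sum of squares about the mean time is Sxx = 78.8/144 = 0.547. A person's fitted slope has variance se²/0.547 + ss² = 1.83·se² + ss². Here se² is residual variance and ss² is true slope variance. The stated SD fixes 2·se² + ss² = 0.11² = 0.0121.

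- If all of it is residual: se² = 0.00605, SD of slope = 0.105, detectable increase 13.8% (14.2% with 52.25 per arm).
- If all of it is true slope variation: SD = 0.110, detectable increase 14.5% (14.9%).

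Over this range, power at a 9.6% increase is 46–51%. In cells, 13.8% of 300 is 41 and 14.9% of 400 is 60 per year. Baseline enters this model as a covariate: it adjusts the level, not the slope, so averaging four baselines does not sharpen this test.

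**4. The same slope test, naive CD4.** If only months 6 and 12 enter, Sxx = 0.125 and the variance is 8·se² + ss², with 2·se² + ss² = 0.0576. The SD is 0.24–0.48 and the detectable increase 34–80% at 55 per arm. With the baseline visit included as an outcome it is 34.3%.

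**5. The average-change reading.** Treat 0.11 and 0.24 as SDs of single-visit differences under compound symmetry, with no true variation in change (assumed).

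- Total: variance factor (1/4 + 1/5)/2 = 0.225, SD = 0.052, detectable increase 6.6%.
- Naive: factor (1 + 1/2)/2 = 0.75, SD = 0.208, detectable increase 29.1%.

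For naive CD4, a baseline-adjusted average has variance 0.0144 × (1 + 2ρ), where ρ is the within-person correlation. It reaches 19.8% only if ρ is about 0.25 or lower (0.62 or lower if 19.8% is a decrease). The plan gives no ρ.

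**6. Direction of the percentage.** Read as decreases, the stated figures are 0.0438/0.11 = 0.398 SD and 0.0958/0.24 = 0.399 SD, the same multiple for both. Section 2.7 calls 9.6% an increase. Converted with 10^d − 1, these shifts are increases of about 10.6% and 25%.

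**The case against.** The strongest defence is that 2.7 does not describe a plain comparison of one yearly change. It describes averages over several visits against averaged baselines, which should do better than 14.5%. For total CD4 this has force. If about 30% of the 0.0121 variance is true change, the factor is 0.30 + 0.70 × 0.225 = 0.4575 and the detectable increase is 9.58%. Entering the four-value baseline mean as a time-zero outcome, with all of the 0.11 as residual error, brings the slope test to about 9.4%. So 9.6% for total CD4 is attainable under some set of assumptions.

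The defence does not carry the pair of figures. Neither route is stated, and section 6 uses baseline as a covariate and tests the slope. Nor does either route give 19.8% for naive CD4, which has one baseline value: a change of means gives 29–34%, depending on how much of the variance is true change.

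The IL-6 calculation has a similar multiplier, 0.3/0.74 = 0.405 SD against 0.534 for the plain test. One undisclosed repeated-measures assumption could therefore lie behind all three figures, and so could one shared error. For CD4, though, averaging should help the two outcomes by different amounts, since total has four baselines and five follow-ups and naive has one and two. A common multiple of 0.40 is thus weak evidence against averaging as the source. This is inference only.

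Two smaller points stand. Section 6 gives no model specific to naive CD4, so applying the slope test there is an extrapolation. And the direction of the percentage matters little for total CD4: 9.6% of 300–400 is 29–38 cells and 10.6% is 32–42, both close to the stated 30–40.

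**Conclusion.** The concern holds. On the stated SDs and n=110, with two-sided alpha 0.05, the detectable increases are 14.5% for total and 34.3% for naive CD4 (14.9% and 35.4% with 5% missing). For the section 6 slope test on total CD4 the figure is 13.8–14.9%, however the 0.11 divides between residual error and true slope variation. The trial would therefore have 46–51% power, not 80%, for the 9.6% increase.

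The total CD4 result rests on alpha and missingness borrowed from IL-6 and on baseline acting as a covariate. The naive result is less firm, because its model is not specified: 34% is the plain figure, about 29% is the change of means under compound symmetry, and the slope figure is larger if only months 6 and 12 enter. Where the printed figures came from cannot be determined from the documents. The point should be fixed, but it does not touch the primary outcome or the basis for n=110.

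**What to change.** Choose one CD4 analysis and make 2.7 and section 6 agree.

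- **If the slope test stays:** restate 2.7 as 80% power for about a 14–15% increase in total CD4 (roughly 41–60 cells per year at a baseline of 300–400), or keep 9.6% and give its power as about 46–51%. For naive CD4, give about 34% as the plain two-sample figure, specify its model, and note that the detectable difference is larger if only months 6 and 12 enter the slope.
- **If average change is intended:** say so in section 6, and recompute both figures from the SD of that averaged quantity and a stated within-person correlation. Under compound symmetry, naive CD4 as a change of means would be about 29%.

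In either case, state alpha and missingness for CD4, convert increases with 10^d − 1, and revise the 30–40 cells per year and 5–8% risk sentences to match. If a repeated-measures variance factor was used, print it and say whether IL-6 used it too.

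The cost is a recalculation and rewording in 2.7, plus one aligning sentence in section 6 if average change is chosen. Enrolment and visits do not change. The drawback is likely to be a less favourable stated figure for a secondary outcome.

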## **3 CLINICAL MANAGEMENT**

### **3.1 Administration of Study Procedures**

Study nurses at each clinical site will be trained prior to study implementation and will perform all study visit procedures during the conduct of the study. The lead physician investigator at each site will conduct clinical and drug toxicity assessments as indicated during the study.

### **3.2 Study Drug Dose Modification**

At baseline, participants will start losartan or matching placebo at 50mg daily. At 2 weeks, side effects and blood chemistries (basic metabolic panel [BMP]) will be assessed. The dose of losartan/placebo will increase to 100mg daily at this week 2 visit (i.e., once lab results return) if all of the following criteria are met:

- a) Systolic blood pressure (BP) ≥90 mmHg

- b) Potassium  $\leq 5.0$  mmol/L
- c) eGFR  $\geq 30$  mL/min/1.73m^2
- d) Lack of a grade  $\geq 3$  side effect since the last evaluation deemed possibly/probably related to the study drug.
- e) Lack of significant side effects deemed related to study drug (e.g., lightheaded upon standing)
- f) Lack of other concerns to increase study drug dosing, as determined by site investigator

If participants are increased to 100mg dose at the week 2 visit and continue to tolerate this dose at the month 1 visit, they will be contacted by phone to verify tolerability 2-4 weeks following the month 1 visit. Participants may be evaluated by clinical labs and/or have side effects assessed at any point during the study, per the discretion of the site investigator. If participants are increased to 100mg daily (or matching placebo) they will maintain this dose for the duration of the 12-month study unless new side effects or adverse events necessitate re-evaluation (see below criteria).

If participants do NOT increase dose to 100mg daily at the week 2 visit (e.g., if symptomatic or if systolic BP is not  $\geq 90$  mmHg), the criteria for dose escalation may be reassessed at the 1-month visit. If participants do not meet criteria for dose increase (from 50mg to 100mg daily) after the 1-month visit, they will be maintained on 50mg dose until the month 3 visit, at which time the dose may be increased to 100mg daily if the five criteria above are met (a-e). At any point when participants have dose increased from 50mg to 100mg, they will be contacted by phone within 2 weeks to assess side effects and have clinical labs drawn to assess toxicity; a full study visit for side effect and adverse event documentation can occur at any point, per the discretion of the site investigator.

Dose Reduction: Tolerability, side effects, and clinical laboratory monitoring will be assessed at each study visit (via participant report and clinical labs), and at any other time point at the discretion of the clinical site investigator. Adverse events that are assessed as related to study drug will prompt re-evaluation via phone or as an adverse event visit, per clinical discretion of the site investigator. If this event worsens or does not resolve after re-evaluation, then study medication dose should be decreased (i.e., from 100mg to 50mg) or stopped (if taking 50mg daily). If signs and symptoms resolve after 2 weeks, then the participant may resume or increase dose (i.e., back to 100mg if previously reduced to 50mg daily), per the clinical discretion of the site investigator.

Stopping Study Medication: If an adverse event of grade  $\geq 3$  is assessed as related to study drug, study medication should be stopped and the participant should be re-evaluated in 2 weeks. If a grade 2 rash is persistent, study medication may also be stopped at the discretion of the site investigator and the participant should be re-evaluated in 2 weeks. If signs and symptoms resolve after 2 weeks, then the participant may be re-challenged at a lower dose (i.e., at 50mg if previously taking 100mg daily) per the clinical discretion of the site investigator. If study medication is stopped for an adverse event that is later determined NOT to be related to study medication, then the

medication may be resumed at 50mg and increased to 100mg per initial criteria for dose escalation and at the discretion of the clinical site investigator.

### **3.3 Adherence and Tolerability**

Adherence will be assessed via participant self-report and pill count (by study nurse) during each follow-up visit. Tolerability will also be assessed via self-report, with additional laboratory assessments performed for toxicity.

### **3.4 Data Collection**

All data will be entered into web-based case report forms and transferred to servers at the data coordinating center (DCC) at University of Minnesota School of Public Health using REDCap software. Paper source documentation will also be kept in a secure, locked location at each clinical site. Study nurses and/or other qualified research technicians will perform all blood draws and blood specimen processing. The blood specimen collection tubes and processing protocols are outlined in the study laboratory manual.

### **3.5 Blood Specimen Processing**

See the LIFE-HIV study laboratory manual for details on blood specimen processing. Participants will be fasting for all study visit blood draws (optional for screening visit). Plasma and serum specimens will need to be processed from whole blood within 4 hours of collection.

### **3.6 Clinical Labs**

All clinical labs will be measured on fresh blood specimens the day of the study visit, at the site clinical lab using CLIA approved standards. Plasma HIV RNA level will be estimated using COBAS® AmpliPrep/COBAS® TaqMan® HIV-1 Test, v2.0.

The following clinical labs will be assessed to monitor for toxicity per Table 2 above:

- i. Complete Blood Count (CBC, with platelet count and differential)
- ii. Basic Metabolic Panel (BMP)
- iii. Hepatic panel (AST, ALT, total bilirubin, alkaline phosphatase)

### **3.7 Plasma Biomarkers**

Plasma specimens will be analyzed at the Laboratory for Clinical Biochemistry Research (U of Vermont), under the direction of [name]. IL-6 will be measured with Chemiluminescent Sandwich ELISA (R&D Systems). A high degree of repeatability (low analytic variability) has been reported by [name] lab for assessing IL-6 and other plasma biomarkers.

### **3.8 Immunologic Phenotypes**

Immunophenotyping will be performed on cryopreserved PBMCs using multi-color flow cytometry at an intramural NIAID/NIH laboratory under the direction of [name].

Panels of fluorochrome-conjugated antibodies for cell surface markers not affected by cryopreservation (e.g., CD3, CD4, CD8, CD38, HLA-DR, CD14, CD16, CD142 or tissue factor (TF) and viability dye to exclude non-viable cells) have been validated previously by [name]. The prevalence of classical (CD14+/CD16-), intermediate (CD14+/CD16+), and non-classical (CD14dim/CD16+) monocyte phenotypes and T cells phenotypes reflecting activation (HLA-DR+/ CD38+) will be characterized; and with these methods additional phenotypes may be easily characterized (e.g. TF expression on monocytes, T-regulatory cells, or senescent T-cells). Only live cells will be included; samples with low (<75%) viability will not be processed.

### **3.9 Lymphatic Tissue Assessment**

Lymph node (LN) biopsy will be performed in a subset of at least 30 participants at baseline and month 12. Criteria for enrollment into the LN substudy include: a) participant consent, b) lack of contraindications to the LN biopsy procedure, and c) palpable lymph nodes on exam by site investigator or research coordinator. All participants at NIH will be offered participation into the LN substudy, and participants at HCMC and Allina/Abbott Northwestern (in Minneapolis) will be offered participation until/if 25 patients are enrolled. Planned analyses will be exploratory in nature focused on assessment of: a) collagen deposition reflecting fibrosis in T-cell zone, b) changes in CD4 T-cell populations, c) changes in the structure of the FRCn, and d) changes in cellular immune activation in lymphatic tissue.

Biopsies will be performed at the University of Minnesota (for HCMC and Abbot Northwestern sites) and the NIH clinical center, by general surgeons using a research facility equipped with inpatient rooms. Tissue specimens are placed into fresh 4% paraformaldehyde for 24 hours and then transferred to 80% ethanol for paraffin embedding. LN tissue can also be divided at the bedside prior to processing to accommodate additional methods that requiring non-fixed tissue.

Changes in LN T-cell zone collagen, the size of T-cell populations, and the FRCn structure will be measured using established methods of IHC with antibody staining and quantitative image analysis (QIA) developed by [name] lab at the University of Minnesota. A similar approach will be used to assess cellular immune activation within lymphatic tissue.

